#### 5.2.1.4. Audit Plan

To evaluate the lack of bias in the investigator's assessment of rPFS, an audit plan will be implemented. The primary audit plan will utilize the method proposed by Dodd *et al* (NCI method). The audit plan proposed by Amit *et al* (PhRMA method) may be implemented as a supportive plan. All scans will be collected in a central location for a blinded independent review.

Stratified simple random sampling will be used to make sure the sample is truly representative of the entire population. 600 (~60%) subjects will be randomly selected for IRC review, stratified by the same factors used for stratified randomization, Gleason score at diagnosis, prior docetaxel use, and geographic region. The SAS code for this is:

```
proc surveyselect data = all_rand method = SRS rep = 1 sampsize = 600 seed = 12345678 out =
random_sample;
```

```
id usubjid;
```

```
STRATA Gleason docetaxel region ;
```

```
run;
```

Based on the audited sample, we can calculate  $\hat{\theta}_{LA}$ , the log(HR) based on INV assessment of rPFS, and  $\hat{\theta}_{CA}$ , the log(HR) based on IRC assessment, and its standard error  $\sqrt{\hat{V}_L}$ . The correlation  $\rho$  between  $\hat{\theta}_{LA}$  and  $\hat{\theta}_{CA}$ , can be estimated through bootstrapping all subjects in the sample with replacement for both INV and IRC. Let  $\hat{\theta}_{L\bar{A}}$  be log(HR) based on the INV assessment of the unaudited sample,  $\delta$  the proportion of the audited sample,  $\sqrt{\hat{V}_L}$  the standard error of  $\hat{\theta}_L$  based on the overall INV evaluation, then we can estimate  $\tilde{\theta}_c$ , Log (HR) for full IRC assessment with this formula:

$$\tilde{\theta}_c = \hat{\theta}_{CA} + \hat{\rho}\sqrt{\delta}(1-\delta)\sqrt{\frac{\hat{V}_{CA}}{\hat{V}_L}}(\hat{\theta}_{L\bar{A}} - \hat{\theta}_{LA}) \quad (2)$$

with variance estimated as  $\hat{V}_{CA} \{1 - \hat{\rho}^2(1-\delta)\}$ . These will be used to verify the investigators' assessment.

100% review of the scans may be done upon the request of HAs or the company's decision. Other supportive methods may be applied to the same sample if appropriate or upon request.

For the selected subjects, scans from discontinued subjects will be centrally reviewed when all scans are available, while scans from ongoing subjects may be centrally reviewed on an ongoing basis when they are available. The latest scans close to or on the date of reaching the prespecified rPFS events will be reviewed after that date. Scans after that date won't be centrally reviewed.

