5. TREATMENT ALLOCATION AND BLINDING

Treatment Allocation

Procedures for Stratification and Randomization

Subjects will be stratified by Gleason score at diagnosis (≤ 7 versus >7), region (North America [NA] and European Union [EU] versus Other Countries), and prior docetaxel use (Yes versus No). Subjects will be randomly assigned to the active or control group in a 1:1 ratio. The randomization will be balanced by using randomly permuted blocks. The interactive web response system (IWRS) will assign a unique treatment code, which will dictate the treatment assignment and matching study drug kit for the subject. The requestor must use his own user identification and personal identification number when contacting the IWRS, and will then give the relevant subject details to uniquely identify the subject.

Blinding

The investigator will not be provided with randomization codes. The codes will be maintained within the IWRS, which has the functionality to allow the investigator to break the blind in the event of an emergency for an individual subject.

Under normal circumstances, the blind should not be broken until completion of the study or the IDMC recommendation for unblinding is accepted by the sponsor. Otherwise, the blind should be broken only if the specific course of action for a safety issue would be dictated by knowing the treatment status of the subject. In such cases, the investigator may in an emergency determine the identity of the treatment by contacting the IWRS. It is recommended that the investigator contact the sponsor or its designee if possible to discuss the particular situation, before breaking the blind. Telephone contact with the sponsor or its designee will be available 24 hours per day, 7 days per week. In the event the blind is broken, the sponsor must be informed as soon as possible. The date, time, and reason for the unblinding must be documented by the IWRS, in the appropriate section of the electronic case report form (eCRF), and in the source document. The documentation received from the IWRS indicating the code break must be retained with the subject's source documents in a secure manner.

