## 1.5. Randomization and Blinding

### 1.5.1. Randomization

Subjects who meet all the inclusion criteria and none of the exclusion criteria will be randomized in a 1:1 ratio to receive apalutamide plus ADT or matching placebo plus ADT using permuted block randomization. Subjects will be stratified by:

- Gleason score at diagnosis ( $\leq 7$  vs.  $>7$ )
- Region (NA/EU vs. Other Countries)
- Prior docetaxel use (Yes vs. No)

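### The audit sampling code in SAP 5.2.1.4 asks for 600 subjects in every stratum, not 600 in total, so it cannot draw the planned audit sample

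*SAP*

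**What the plan says.** SAP 5.2.1.4 sets up an audit to check for bias in the investigator's reading of rPFS. The text gives a total and a share: "600 (~60%) subjects will be randomly selected for IRC review, stratified by the same factors used for stratified randomization". It also gives the aim: "Stratified simple random sampling will be used to make sure the sample is truly representative of the entire population".

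The SAS code offered as the implementation is "proc surveyselect data = all_rand method = SRS rep = 1 sampsize = 600 seed = 12345678" (an output data set is then named), with the statement "STRATA Gleason docetaxel region". There is no allocation option, sampling rate, list of stratum sizes or select-all option.

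The estimator that follows, equation (2), combines the centrally read log(HR) in the audited subjects with the difference between the unaudited and audited investigator log(HR). It uses one audited proportion, delta, and no stratum weights. The same section allows a review of all scans on request, as an option and not as the plan. Nothing elsewhere in the SAP or protocol says how the 600 are to be divided among the strata.

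**The concern.** The text treats 600 as the total for the trial. The code, read by the usual rules of the procedure, treats 600 as the size for each stratum. Fixing a seed and printing the code in the SAP presumably serves to make the selection reproducible and free of discretion. That purpose is lost if the code cannot run, because the sample must then come from a program written later.

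The draw matters for three reasons:

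- The audit is the SAP's stated check on bias in investigator-assessed rPFS, which is a dual-primary endpoint.
- The draw decides whose scans are read centrally, and that reading may proceed on an ongoing basis.
- The sensitivity analysis in SAP 5.2.1.5 also relies on central review data.

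**Working it through.** **Inputs.** About 1,000 subjects randomised (SAP 1.2). An audit sample of 600, about 60% (SAP 5.2.1.4). Three stratification factors with two levels each: Gleason score, region and prior docetaxel (SAP 1.5.1; Protocol section 5). Stratum sizes are not given in the documents.

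**1. The plan's own figure.** 600 / 1,000 = 0.60. The text is consistent with itself.

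**2. What the code requests.** Strata: 2 × 2 × 2 = 8. With a single size, a STRATA statement and no allocation option, the size applies per stratum. The request is 8 × 600 = 4,800, which is 4,800 / 1,000 = 4.8 times the number randomised.

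**3. Whether it can be met.** 1,000 / 600 = 1.67, so at most one stratum can contain 600 subjects. If all 8 strata are occupied, at least 7 are too small for a simple random sample of 600 without replacement. This does not depend on how the subjects are divided: whenever more than one stratum is occupied, at least one is short. The code would return exactly 600 only if every subject fell in a single stratum.

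**4. What equation (2) expects.** Write V_L for the variance of the investigator log(HR) in all subjects. If information is proportional to the number sampled, the audited part has variance V_L/δ and the unaudited part V_L/(1−δ). Their difference has variance V_L/[δ(1−δ)]. Its covariance with the centrally read audited estimate is −ρ√(V_CA·V_L/δ). The optimal weight on the difference is therefore

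ρ√(V_CA·V_L/δ) × δ(1−δ)/V_L = ρ√δ(1−δ)√(V_CA/V_L),

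and the resulting variance is V_CA{1 − ρ²(1−δ)}. Both agree with the SAP, so the formula is not at fault. With one δ and no weights, it fits a sample drawn at about the same rate in each stratum.

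**5. If a select-all option were added.** The draw becomes the sum over strata of min(600, N_h).

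- If every stratum is below 600, everyone is selected, δ = 1 and the weight √δ(1−δ) is 0. The central log(HR) is observed directly. This is the full review that the SAP permits.
- If one stratum exceeds 600 (assumed 770, with 230 elsewhere), the draw is 600 + 230 = 830. That stratum is sampled at 600/770 = 78% and the rest at 100%.

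Neither case is the 600-subject audit that was planned.

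**6. After the fix.** Proportional allocation gives 0.6 × N_h per stratum. For an assumed layout of 20, 13, 178, 119, 40, 27, 362 and 241 (total 1,000), the targets are 12.0, 7.8, 106.8, 71.4, 24.0, 16.2, 217.2 and 144.6, which sum to 600. A rate of 0.6 rounded up in each stratum gives 12 + 8 + 107 + 72 + 24 + 17 + 218 + 145 = 603. In general, rounding up adds less than one subject per stratum, so fewer than 8 in all and a total of at most 607.

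**The case against.** The strongest reply is that the prose already fixes the design. A total of 600, a share of about 60% and an aim of representativeness point naturally to about 60% in each stratum. On that view the defect is one missing option in a code fragment. It would announce itself as a failed run, and any programmer would put it right. The audit is supportive: the primary rPFS analysis is the stratified log-rank test at 0.005 on investigator assessments in all ITT subjects, which this code does not touch. The SAP also allows other supportive methods and a full review.

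Most of this stands and limits the point. It does not remove it. The prose never names proportional allocation, and different repairs give different samples, as step 5 shows. The choice between them belongs in the plan.

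A reader might infer more: that the code biases the audit, that selecting all subjects in short strata must over-represent small strata, or that equation (2) is wrong whenever sampling rates differ. The documents do not support these readings.

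- The code draws no sample, so by itself it biases nothing.
- Selecting all gives a complete review if every stratum is below 600. Unequal rates arise only if one stratum exceeds 600.
- If the audit uses the stratified Cox model of SAP section 5, with its common hazard ratio, unequal rates mainly affect precision and the weight and variance that depend on δ. A systematic shift needs the treatment effect, or the disagreement between investigator and central reading, to differ by stratum. The documents give no figures on either.

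**Conclusion.** The point holds as a mismatch between text and code that should be corrected. The text plans 600 subjects in total. The code requests 600 in each of up to 8 strata, or 4,800 from about 1,000, and so cannot deliver the prespecified sample with the prespecified seed. The consequence is loss of prespecification for the audit draw. The validity of the primary rPFS test is not in question, and no bias in the audit has been shown.

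The conclusion rests on two features of standard SAS behaviour that the documents do not state and that I have not run: a single sample size applies per stratum when no allocation is given, and an oversized request without replacement ends in an error. It does not rest on any assumed stratum sizes, only on subjects being spread over more than one stratum.

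**What to change.** Keep `sampsize = 600` as the total, add `/ alloc = prop` at the end of the STRATA statement, and sort the input data set by the three strata variables before the call. State in the text that allocation is proportional across the strata and how fractional stratum sizes are rounded. Replacing the size with `samprate = 0.6` is an acceptable alternative if a total slightly above 600 (at most 607) is acceptable; the text should then describe 600 as approximate. Run the revised code on a dummy data set before it is finalised.

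The cost is one line of code and a sentence of text. Sample size, endpoint definitions and equation (2) need no change.

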#### 5.2.1.5. Sensitivity analysis for the rPFS

Per FDA's request, a sensitivity analysis for rPFS will be performed based on the central review data, where the date of progression is defined as the date of the scan showing  $\geq 2$  new bone lesions compared to the nadir of bone lesions.

#### 5.2.2. Dual-Primary Endpoint of OS

The efficacy endpoint of OS is defined as the time from date of randomization to date of death from any cause. Subjects alive at time of analysis will be censored on the last date the subject was known to be alive.

The primary analysis for the comparison of the OS distributions between the two treatment groups will be carried out using the stratified log rank test at a two-sided significance level of 0.045. The analysis methods for OS will be similar to those outlined for the analysis of rPFS (see Section 5.2.1.3). In addition, 2-year, 3-year survival rates will be estimated using the Kaplan-Meier method. Subgroup analyses on subjects with low- or high-volume mHSPC disease will be performed without alpha spending assigned.

### 5.3. Secondary Endpoints

The analyses of the secondary endpoints will be performed at the time of the primary analysis of the dual-primary endpoint of rPFS and the first interim analysis of the dual-primary endpoint of OS using similar methods as the dual-primary endpoints, and the significance of secondary endpoints can be claimed only if both rPFS and OS are significant.

This procedure controls the overall level of significance at the 2-tailed, with  $\alpha$  set at 0.05. Subgroup analysis (for high volume and low volume mHSPC subgroups) on the secondary endpoints may be performed for exploratory purposes.

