9.2.3. Endpoints

The primary and secondary endpoints described below will be used to demonstrate clinical benefit.

Dual-Primary Endpoints

The dual-primary endpoints are rPFS and OS.

rPFS

Radiographic progression-free survival, as assessed by the investigator is defined as the duration from the date of randomization to the date of first documentation of radiographic progressive disease or death due to any cause, whichever occurs first.

Radiographic progressive disease in this protocol is defined as one of the following:

- Progression of soft tissue lesions measured by CT or MRI as defined by modified RECIST 1.1 ([Attachment 1](#))
- A subject is considered to have radiographic progression by bone scan if:
 - 1. Subjects who are observed to have ≥ 2 new bone lesions on the Cycle 3 bone scan compared with the baseline bone scan will need to have a confirmatory bone scan performed at ≥ 6 weeks later and their scans will be subjected to the 2+2 rule as follows:
 - Subjects with a confirmatory scan that shows ≥ 2 new bone lesions compared with the Cycle 3 bone scan (ie, at least 4 new lesions compared with the baseline bone scan) will be considered to have radiographic progression by bone scan. The date of progression will be the date of the Cycle 3 bone scan.
 - Subjects who have a confirmatory scan that does not show ≥ 2 new bone lesions compared with the Cycle 3 bone scan will not be considered to have radiographic progression by bone scan. In order to be considered to have radiographic progression by bone scan, these subjects will need to have a subsequent bone scan with observation of ≥ 2 new bone lesions compared with the Cycle 3 bone scan. The date of progression would be the date of the FIRST subsequent bone scan with ≥ 2 new bone lesions compared with the Cycle 3 bone scan.
 - 2. Subjects whose Cycle 3 bone scan does not show ≥ 2 new bone lesions compared with baseline bone scan will not need to have a confirmatory bone scan performed and will not be considered to have radiographic progression by bone scan at that time. In order to be considered to have radiographic progression by bone scan, these subjects will need to have a subsequent bone scan with ≥ 2 new bone lesions compared with the baseline bone scan. The date of radiographic progression by bone scan will be the date of the FIRST subsequent bone scan with ≥ 2 new bone lesions compared with the baseline bone scan.

OS

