### **1.4. Sample Size Justification**

An overall type I error of 5% is planned for this study. This study utilizes the dual-primary endpoints of rPFS and OS with a 0.005 level of significance allocated for the rPFS endpoint and 0.045 is allocated for OS.

It is assumed that the failure distribution of the dual-primary endpoint of rPFS follows an exponential distribution with a constant hazard rate. It is estimated that approximately 368 rPFS events would be required to provide at least 85% power in detecting a hazard ratio (HR) of 0.67 (median rPFS of 20 months for the control group [ADT] versus 30 months for the treatment group of apalutamide plus ADT) at a 2-tailed significance level of 0.005. The assumption of 20 months for the control is an estimate based on published data.

The study will also provide sufficient power (approximately 80%) to detect a HR of 0.75 in the dual-primary endpoint of overall survival (OS) based on an assumed OS median of 44 months for the control group (ADT) (i.e., 44 months versus 59 months). Approximately 410 death events will be required to detect the assumed HR at a 2-tailed significance level of 0.045 with enrollment duration of

approximately 30 months (approximately 1,000 subjects). The total study duration will be approximately 54 months to obtain 410 deaths.

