## **5.1. Analysis Specifications**

### **5.1.1. Level of Significance**

In general, a two-sided significance level of  $\alpha = 0.05$  will be used for all hypothesis testing and all CIs will be calculated on the two-sided 95% confidence level, unless otherwise specified.

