### 5.3.3. Analysis Methods

The testing of these secondary efficacy endpoints will be based on the stratified log rank test. Secondary efficacy endpoints will be summarized using the Kaplan-Meier method and displayed graphically where appropriate. Cox proportional hazard models will be used to estimate the HR and its 95% confidence interval.

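### As visible, SAP 5.3 claims overall control at 0.05 for four secondary endpoints, but the gate it describes does not control error among the four

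*SAP*

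**What the plan says.** SAP 1.4: "An overall type I error of 5% is planned for this study", with a "0.005 level of significance allocated for the rPFS endpoint and 0.045 is allocated for OS". SAP 5.2.2 tests OS by a "stratified log rank test at a two-sided significance level of 0.045".

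SAP 5.3 places the secondary analysis at the rPFS primary analysis and first OS interim, and adds the gate: "the significance of secondary endpoints can be claimed only if both rPFS and OS are significant". The next paragraph opens "This procedure controls the overall level of significance at the 2-tailed" and sets that level at 0.05.

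The four endpoints are time to pain progression, SRE, chronic opioid use and cytotoxic chemotherapy (SAP 5.3.1). On method, SAP 5.3.3 says "The testing of these secondary efficacy endpoints will be based on the stratified log rank test" and adds Kaplan-Meier and Cox estimates. SAP 5.1.1 gives a general default: two-sided 0.05 "will be used for all hypothesis testing and all CIs will be calculated on the two-sided 95% confidence level", unless another level is specified. Protocol 11.3.3 adds only the timing and that the methods resemble those for the primaries. Protocol 9.2.3 gives these endpoints a confirmatory role: "The primary and secondary endpoints described below will be used to demonstrate clinical benefit".

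**The concern.** A gate answers one question: may the secondary family be tested at all? If either primary null is true, a false secondary claim requires a false primary claim first, so it is already counted in the 5% for the primaries. If the drug truly improves both rPFS and OS, the gate gives no such protection. Four tests then remain, and something must limit the error among them. No visible sentence does.

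What is at stake is which secondary claims may be made. The SAP speaks of claiming significance and attaches an explicit error guarantee. For an endpoint with a p-value between 0.0125 and 0.05, the visible text does not settle whether the claim stands under that guarantee, and a rule chosen after the results are known would weaken it.

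**Working it through.** **Inputs from the documents.** Alpha 0.005 (rPFS) and 0.045 (OS); 368 rPFS events, HR 0.67; 410 deaths, HR 0.75, about 80% power; first OS interim at about 205 deaths; four secondary endpoints. The cumulative OS alpha of 0.0091 at the first interim and 0.0224 at the second comes from the protocol's Amendment 4 log, because the current text is blacked out.

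**Assumptions.** Each secondary is tested at two-sided 0.05, inferred from the SAP 5.1.1 default. The documents give no correlation ρ between endpoints, so a range is shown. Some positive correlation is built in, because pain progression includes the start of chronic opioids.

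**1. The plan's own figures.** 0.005 + 0.045 = 0.05, so the dual-primary split reproduces. Power is Φ(|ln HR|·√D/2 − z), with z the two-sided critical value.
- rPFS: 0.4005 × √368/2 = 3.841; 3.841 − 2.807 = 1.034; power 84.9% (stated: at least 85%).
- OS at 410 deaths: 0.2877 × √410/2 = 2.913; 2.913 − 2.005 = 0.908; power 81.8% before any cost of the interim looks (stated: about 80%).

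**2. Secondary family, gate open.** If independent, the error with k true nulls is 1 − 0.95^k:
- k = 1: 5.0%
- k = 2: 9.75%
- k = 3: 14.3%
- k = 4: 18.5%; the Bonferroni bound is 4 × 0.05 = 20%

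With correlation, take Z_j = √ρ·W + √(1−ρ)·E_j and find the chance that any |Z_j| exceeds 1.96:

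| ρ | 0 | 0.3 | 0.5 | 0.7 | 0.9 |
|---|---|---|---|---|---|
| all four null | 18.5% | 17.4% | 15.6% | 13.0% | 9.4% |

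With two nulls at ρ = 0.5 the figure is 9.1%. The stated 5% is reproduced only when a single secondary null is true.

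**3. Unconditional error under the design effects, all four secondaries null.** This depends on when the gate is judged.

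*OS may succeed at any look.* With the stated 80% OS power and rPFS and OS independent, the gate opens with probability 0.849 × 0.80 = 0.68. At ρ = 0 the error is 0.68 × 0.1855 = 12.6%. In a simulation with a common ρ across the two primaries and the four secondaries, the error is 12.6%, 11.5%, 9.7% and 7.3% for ρ = 0, 0.3, 0.5 and 0.7. A repeat of that simulation gives 4.7% at ρ = 0.9.

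*Gate judged only at the first OS interim.* OS power there: 0.2877 × √205/2 = 2.059; 2.059 − 2.608 = −0.549; power 29.2%. The gate opens with probability 0.849 × 0.292 = 0.248. Error with the secondaries independent of the primaries:
- ρ = 0: 0.248 × 0.1855 = 4.6%
- ρ = 0.5: 0.248 × 0.156 = 3.9%
- ρ = 0.7: 0.248 × 0.130 = 3.2%

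If rPFS and OS were fully dependent, the ceiling at ρ = 0 would be 0.292 × 0.1855 = 5.4%. If the common ρ also links the primaries to the secondaries, the repeat simulation (2,000,000 draws) gives 5.3%, 5.8%, 5.9% and 4.7% for ρ = 0.3, 0.5, 0.7 and 0.9.

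**4. After the fix** (gate open, four nulls, ρ from 0 to 0.9). A fixed order gives 5.0%. Hochberg gives 4.9% to 3.0%. Bonferroni or Holm gives 4.9% to 2.6%.

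**The case against.** A reader might infer that the plan has no rule and that the control sentence is simply false. The documents do not support that. The Hochberg paper is reference 9 in the SAP, yet no visible sentence cites it. Visible citations run in order of first use: 7 and 8 in SAP 5.2.1.4, then 10 to 12 in SAP 5.4.3. Reference 9 therefore belongs in the stretch that contains 5.3. The fallback paper (reference 18) is also uncited in the visible SAP, and multiplicity text is blacked out in SAP 3.1 and Protocol 11.3.2. The sentence about controlling the level opens a new paragraph and may have lost what it referred to. So a rule may have been removed.

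That is plausible but not shown. SAP 5.3 carries no mark of removed text, while the other two places do. References 14 and 15 are uncited too, so a listed reference need not be a method in use.

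Two further objections stand. First, testing each endpoint at 0.05 is an inference from a default that allows exceptions; SAP 5.3 itself states 0.05 only for the overall level. Second, a reader might take 18.5% as the trial's error rate. It is a worst case: independent endpoints, gate open, and no effect on any secondary despite real effects on both primaries. Under the design effects, a gate judged only at the first OS interim brings the error to about the stated level. That does not rescue the guarantee, because larger primary effects open the gate more often and move the error towards the figures in step 2.

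**Conclusion.** The point holds as a gap between a stated property and the visible procedure. The gate alone does not deliver 0.05 across the four secondary endpoints.

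- **Gate open, each tested at 0.05:** about 9% to 19% with all four null (correlation 0.9 to 0), and about 9% to 10% with two null (correlation 0.5 to 0).
- **Unconditional, design effects, OS at any look:** about 7% to 13% (correlation 0.7 to 0).
- **Unconditional, design effects, first OS interim only:** below 5% if the primaries are independent of each other and of the secondaries. Without that independence it can pass 5% slightly, to about 6%.

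All of this rests on the 0.05 default applying to each endpoint, on assumed correlations, and on interim levels taken from the amendment log. Whether a withheld rule closes the gap cannot be decided from the public text. The rPFS and OS tests are unaffected.

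**What to change.** In SAP 5.3, state one procedure for the four secondary endpoints at overall two-sided 0.05, or confirm it if withheld text already specifies one. Either of these would serve:
- a fixed order, named in the text, stopping at the first non-significant result; or
- the Hochberg procedure, which is already in the reference list and relies on the positive dependence that is plausible here.

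In the same place, state at which OS look the gate is judged, since the secondary analysis is tied to the first interim but OS may become significant later. P-values that do not pass, or are not reached, should be called nominal. If no procedure is intended, delete the sentence on controlling the overall level and label all secondary p-values nominal.

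The change is SAP wording only. The cost is that an endpoint with a p-value between 0.0125 and 0.05 may no longer be claimable on its own; under a fixed order, an endpoint placed after a failed one cannot be claimed at all.
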